6. STUDY PROCEDURES

6.1 Schedule of Evaluations

Assessment	Enroll / Screen (W-4 to 0) ≤ 4 Weeks BEFORE Baseline	Randomize (W-4 to 0) ≤ 4 Weeks BEFORE Baseline	Baseline (W0) ≤ 2 Weeks BEFORE Treatment	Post-Treatment (W4-5) ≤ 2 Weeks AFTER Treatment	Six-Month Follow-up (W30) ±2 Weeks of 6-Months Post-Tx	12-Month Follow-up (W56) ±2 Weeks of 12-Months Post-Tx	Lost to Contact OR Dropped From Treatment
Informed Consent Form	X						
Demographics	X						
Health Questionnaire			X	X	X	X†	
Health Questionnaire Addendum			X	X	X	X	
Inclusion/Exclusion Criteria	X						
Enroll/Screen	X						
Randomize		X					
Concomitant Medications			X	X	X	X	X
Adverse Events			X	X	X	X	
Oswestry Disability Index	X		X	X	X	X	X
Quick Drinking Screen (QDS)			X	X	X	X	
Fagerstrom Test for Nicotine Dependence (FTND)			X	X	X	X	
Fagerstrom Test for Nicotine Dependence – Smokeless Tobacco (FTNB-ST)			X	X	X	X	
PROMIS Short Form	X		X	X	X	X	
Timeline Followback Interview	X		X	X	X	X	X
Ohio State University TBI Scale Short Form – VA	X						
Patient Health Questionnaire – 9 (PHQ-9)	X		X	X	X	X	

Assessment	Enroll / Screen (W-4 to 0) ≤ 4 Weeks BEFORE Baseline	Randomize (W-4 to 0) ≤ 4 Weeks BEFORE Baseline	Baseline (W0) ≤ 2 Weeks BEFORE Treatment	Post-Treatment (W4-5) ≤ 2 Weeks AFTER Treatment	Six-Month Follow-up (W30) ±2 Weeks of 6-Months Post-Tx	12-Month Follow-up (W56) ±2 Weeks of 12-Months Post-Tx	Lost to Contact OR Dropped From Treatment
PTSD Checklist – 5	X		X	X	X	X	
Functional Capacity Evaluation			X	X	X	X	
Pain Catastrophizing Scale			X	X	X	X	
Fear Avoidance Beliefs Questionnaire			X	X	X	X	
Chronic Pain Acceptance Questionnaire			X	X	X	X	
Multidimensional Pain Inventory			X	X	X	X	
Generalized Anxiety Disorder – 7 item (GAD-7)			X	X	X	X	
Depressive Symptom Inventory-Suicidality Subscale	X		*	*	*	*	
Current Opioid Misuse Measure			X	X	X	X	
Mini International Neuropsychiatric Interview	X						
Actiwatch			X	X	X	X	
MEMS eCap			X	X	X	X	
Treatment Helpfulness Questionnaire				X			
Subjective Opiate Withdrawal Scale			X	X	X	X	
Pain Diary	X		X	X	X	X	
Interpersonal Needs Questionnaire (Burdenomeness Items)	X		X	X	X	X	
Phone Contact (Adherence / AE / MEMS-Actiwatch)*					X*	X*	
Pregnancy Test	X						

Assessment	Enroll / Screen (W-4 to 0) ≤ 4 Weeks BEFORE Baseline	Randomize (W-4 to 0) ≤ 4 Weeks BEFORE Baseline	Baseline (W0) ≤ 2 Weeks BEFORE Treatment	Post-Treatment (W4-5) ≤ 2 Weeks AFTER Treatment	Six-Month Follow-up (W30) ±2 Weeks of 6-Months Post-Tx	12-Month Follow-up (W56) ±2 Weeks of 12-Months Post-Tx	Lost to Contact OR Dropped From Treatment
Medication Quantification Scale – Version III	X		X	X	X	X	
Prescription Access in Texas						X [†]	
Missing Data Assessment							X

*Occurs monthly after the post-treatment visit

† To assess opioid prescriptions dispensed for the past year

Figure 3. Flowchart: Recruitment to Randomization

[figure not shown]
[figure not shown]

Figure 4. Flowchart: Enrollment to Assessment

6.2 Description of Evaluations

6.2.1 Enrollment and Screening Evaluation (Week -4 to Week 0; See Figure 3)

All screening will occur within 4 weeks after consent (so consent occurs at Week -4)

Consenting Procedure

Potential participants will have the study explained to them in a safe and private location. The Veteran will be given a copy of the informed consent document (ICD) to read. The research team member obtaining informed consent will then engage the Veteran in an interactive explanation of the study guided by the Informed Consent Form. After the Veteran has read the ICD, they will be given the opportunity to consider participation and discuss the research with other family and friends. The Research Team will be available to answer any questions about the research. Once the potential participant has reached a decision, the advising staff member will review the risks and benefits of study participation and ensure the Veteran has an understanding of the material discussed, and the risks and benefits of their potential involvement in the study. The advising staff member will have the participant sign the consent form. A copy of the signed ICD will be given to the Veteran. STRONG STAR addresses issues related to mental capacity of potential participants through ongoing screening procedures using trained independent evaluators. Any concern that a potential participant is unable to comprehend what is being asked of them to participate in the research or the consent document will be referred to a licensed psychologist for additional assessment. Similarly, any concerns identified during the course of the study that participants may no longer comprehend what is being asked of them or be able to engage in the study procedures will be referred to a licensed psychologist and the research team. All Veterans who have provided informed consent will be considered enrolled to the study. Consent will be tracked for each participant using the NCCIH Screening and Enrollment Log (**Appendix A3**).

Screening

All participants will be screened **after** consent (i.e., enrollment) and screening will be tracked by the Coordinator and Research Assistant using the STRONG STAR Screening Form, see **Appendix H**). Initial contact will either be made with the participating Veteran directly (in response to an advertisement of flyer, the Veteran will contact a member of the research team) or on referral from the Veteran's STVHCS provider in the PRC, Pain Management Clinic, PTSD Clinical Team, or Primary Care Clinic. Each clinic where we recruit for this research will be given a list of inclusion and exclusion criteria for this research. After providing informed consent, each Veteran will be screened to confirm their suitability for participation in this research. Those who are found to be ineligible for this research study will be disenrolled from the study as a "screen failure" and this will be tracked using the NCCIH Screening and Enrollment Log. Screening will be completed by an Independent Evaluator (IE) and a Clinical Psychology Fellow or Intern (who will complete the clinical interview). The following assessments, assessment windows, and inclusion thresholds must be completed as part of screening:

Assessments (Inclusion Criterion)	Assessment Window	Inclusion Threshold
Clinical Interview PROMIS – SF (Deployment-Related Chronic Musculoskeletal Pain; CMP)	Within 4 weeks after enrollment	Veteran must report pain that has interfered in daily functioning more days than not for the past 3 months CMP must be related (e.g., exacerbated or cause by) to OEF/OIF/OND deployment Service Member must not be currently engaged in treatment specifically targeting opioid use Veterans not on opioid medication were referred by any of their VA medical providers.
Oswestry Disability Index (Moderate Disability)		Veteran must score $\geq 20\%$ disability for enrollment
Timeline Follow-back Interview (Persistent Opioid Use)		Veteran must report using opioid medication for 20 out of 30 days for the past 3 months
Patient Health Questionnaire - 9 (Moderate Depression or PTSD)		Pain must present in the context of depression (based on a PHQ-9 Score of 10 or more) or PTSD
PTSD Checklist – 5 (Moderate Depression or PTSD)		Pain must present in the context of PTSD (based on a PTSD Checklist Score of 25 or more) or depression
Depressive Symptom Inventory-Suicidality Subscale (No active suicidal ideation or intent)		Veterans cannot enroll if they report suicidal ideation with intent. There is no widely accepted cutoff score for this on the BSSI, so any

		positive BSSI score will need to be reviewed by the PI and Psychologist Co-Investigators and the PI will make a decision on inclusion
Ohio State University TBI Scale Short Form – VA		Veterans cannot participate with severe TBI-related cognitive impairment
(No severe TBI-related cognitive difficulty)		
MINI (Psychosis Module)		Screen out psychosis
Pregnancy Test		Screen for pregnancy

The outcome of all screening will be briefed to the PI and Co-Investigators during a weekly study meeting (in a de-identified format) for a final determination of each enrolled participant’s eligibility for the study. Once confirmed eligible, participants are randomized. The PI will adjudicate any unclear determinations of eligibility for enrollment and the determination will be entered into the enrollment log.

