AIM 2: Assess the efficacy of FORT-A for decreasing the rate of opioid recidivism (using any opioid for 3 or more days in any 30-day period) compared to standard PRC care in a sample of OEF/OIF/OND polymorbid CMP Veterans discharged off of opioid medication in VA care since the start of the OSI. Unlike the original FORT trial, this research will formally and prospectively track opioid medication use among polymorbid Veterans to sensitively detect changes in chronic opioid therapy attributable to FORT-A versus PRC treatment. FORT-A is expected to produce significant reductions in the rate of opioid recidivism by imparting numerous strategies to supplant opioid medication as a pain management strategy. FORT-A will avoid the stigma of “traditional” opioid abuse treatment and provide a pain management alternative to those who have been discharged from opioid medications as part of the OSI.

EXPLORATORY AIM 3: Based on the PI’s ongoing ESCAPE trial, this research team has identified psychological processes (helplessness, perceived burdensomeness) that likely play a mechanistic role in pain management among OEF/OIF/OND deployers. We will assess these constructs twice a week and analyze latent changes in FORT-A and PRC Veterans to ascertain their role as pain management mediators

Design and Outcomes

This study is a 1:1 block randomized clinical trial comparing the FORT-A program to treatment as usual for polytrauma OEF/OIF/OND Veterans with prior persistent opioid use and chronic musculoskeletal pain who are eligible for treatment through the STVHCS Polytrauma Rehabilitation Center. All participants will be offered Physical Therapy services before enrollment and will be enrolled after completing or denying Physical Therapy (up to 12 sessions as recommended by a PRC Physical Medicine & Rehabilitation Physician ([name], [name]). If they have already completed PRC Physical Therapy before study enrollment, they will not need to do so again. Also, if the Veteran qualifies but refuses PRC Physical Therapy, he or she will still be eligible to enroll in this study and will not be asked to complete PRC PT. Veterans randomized to PRC (treatment as usual) will then meet with PRC and other VA medical providers per usual standards of care (described below). Those

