- Display at least moderate disability based on an Oswestry Disability Index score

- of 20% or greater
- Primary pain complaint was acquired or exacerbated due to military service or a deployment-related injury
- Chronic musculoskeletal pain presents in the context of comorbid psychiatric trauma condition(s) including: mild TBI, PTSD, and/or depression
- Present with a history of persistent opioid use (using opioid medication for 20 out of every 30 days over the past three or more months) and discontinued from opioid medications at the request of their VA provider (e.g., as part of the VA Opioid Safety Initiative [OSI]).
- Speak and read English proficiently
- Eligible to become or are currently enrolled as a STVHCS PRC patient

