The FORT program was originally tested in a non-polymorbid active duty military chronic pain sample. The original trial showed that our model of integrated care can effectively improve physical and psychosocial disability among military service members with pain. It has yet to be tested in a polymorbid pain population, but we believe that the CAM-based composition of FORT makes it an excellent substrate for polymorbid pain management. We have expanded on the original FORT trial through several subsequent trials specifically focusing on pain processes in polymorbid military members and Veterans. Data from these subsequent trials have allowed us to tailor the FORT intervention to the specific needs of a polymorbid OEF/OIF/OND Veteran chronic pain population. We have labeled this amended version of the manualized program “FORT-A” (A = Amended), and believe that this new program offers the best available opportunity for polymorbid pain management. The proposed study will recruit 130 OEF/OIF/OND Veterans with polymorbid chronic musculoskeletal pain who are currently using chronic opioid therapy for pain (taking opioid medications daily for 20 out of 30 days a month for three or more months). In 2015, the VA Opioid Safety Initiative (OSI) began to programmatically work toward improving the safety of opioid medication prescription for San Antonio Veterans with chronic pain. As noted above, very little is known about the potential outcomes of this initiative, but the scant available data suggest a rate of opioid recidivism of 30-40% among prior persistent opioid users who get no specialty intervention. To align with this initiative, this study altered the opioid inclusion criterion to include Veterans who were removed from opioid medications during the OSI. These Veterans will be randomly assigned to either the 3-week interdisciplinary FORT-A chronic pain management program (described below) or to

treatment in the South Texas Veterans Health Care System’s (STVHCS) PRC in San Antonio, TX, which represents the best available care for Veterans with deployment-related polymorbid pain. Primary endpoints for this research include pain management (represented in Aim 1) and opioid use (represented in Aim 2) at pre-treatment, post-treatment, 6-month follow-up and 12-month follow-up.

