4. SELECTION AND ENROLLMENT OF PARTICIPANTS

Participants for this research will include (N=130) U.S. military Veterans treated through the South Texas Veterans Health Care System (STVHCS) for chronic musculoskeletal pain associated with deployment to OEF/OIF/OND (see *Inclusion/Exclusion Criteria* below). Eligible Veterans can have multiple pain concerns, but their primary pain concern must be musculoskeletal pain. All eligible Veterans must be a prior persistent opioid user who was removed from their opioid medication by their VA provider. Participants will be recruited through the STVHCS Polytrauma Clinic, the STVHCS Pain Management Service, and the STVHCS Primary Care Service. They will be eligible for care in the PRC. Our PRC partners estimate that they enroll approximately 30 new patients at the PRC per month, roughly 80% of whom would meet criteria for this research. We will recruit through direct provider referrals and advertisements posted in VHA clinics; both of these strategies have been quite successful in both the original FORT trial and our ongoing STRONG STAR research efforts. Our PRC collaborators ([name] and [name]) will ask their staff to introduce the study to new PRC patients and will be available to answer questions. This research has been adopted as a STRONG STAR initiative, and will have access to STRONG STAR resources and procedures for recruitment. This will be of significant benefit because STRONG STAR studies routinely achieve their recruitment targets through local advertising, media exposure for the consortium, and solid working alliances with VHA and DoD service providers. Based on our experience with numerous STRONG STAR trials and the original FORT trial, we expect <30% attrition and have factored this into our recruitment target. Participants will be reimbursed for time and travel.

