4.1 Inclusion Criteria

Study participants must meet all of the inclusion criteria below to participate in this study as follows:

- 1) Demographics for inclusion in this research include both genders, all racial/ethnic groups, and ages 18-72.
- 2) Present with chronic musculoskeletal pain (CMP) as a primary pain complaint
- 3) CMP is accompanied by at least moderate disability based on a score of 20% or more on the Oswestry Disability Index;
- 4) Consistent with NIH Task Force recommendations, "chronic" CMP has been a problem for the Veteran for at least half the days in the last 3 months and was acquired or exacerbated as part of active duty U.S. military service in the Gulf War, Operations Iraqi Freedom (OIF), Enduring Freedom (OEF), or New Dawn (OND) war eras.
- 5) CMP presents in the context of comorbid psychiatric symptoms of posttraumatic stress disorder (PTSD; based on a score of 25 or more on the PTSD Checklist-Version 5) and/or depression (based on a score of 10 or more on the PHQ-9).

6) Demonstrate prior “chronic” opioid use (defined as using opioid medication for 20 out of every 30 days over three or more months) and discharged off of persistent opioid medications on their own or by a provider for at least one week prior to the pain management program period (Weeks 1-3).

7) Speak and read/understand English well enough to fully participate in the intervention and to reliably complete assessment measures.

8) The Veteran will be eligible to be a PRC patient (i.e., have multiple trauma related physical and psychological injuries; VA, 2013) and be eligible for Physical Therapy referral through the PRC (though the referral for the same service could also come from another VHA provider). All participants will be offered Physical Therapy services before enrollment and will be enrolled after completing or denying Physical Therapy.

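### The eligibility text contradicts itself twice: pain tied only to Gulf War service is admitted and excluded, and the opioid screening row fails Veterans whom criterion 6 admits

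*Combined protocol and SAP*

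**What the plan says.** **Service era.** Inclusion 4 in Section 4.1 lists the Gulf War beside OIF, OEF and OND, and service in any one of these eras is enough. Exclusion 3 in Section 4.2 removes pain with no link to service in the OEF/OIF/OND eras, and meeting any one exclusion removes the candidate. The clinical interview row of the Section 6.2.1 screening table requires a link to OEF/OIF/OND deployment. The Precis, Section 3, the opening of Section 4 and the aims in Section 9.6 also name OEF/OIF/OND only.

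**Opioid status.** Section 6.2.1 makes the thresholds in its table a mandatory part of screening. The TLFB row reads "Veteran must report using opioid medication for 20 out of 30 days for the past 3 months". Criterion 6 in Section 4.1 instead asks for a past period of chronic use, and then that the Veteran be "discharged off of persistent opioid medications on their own or by a provider for at least one week prior" to programme Weeks 1-3. The interview row of the same screening table expects some candidates to be off opioids already: "Veterans not on opioid medication were referred by any of their VA medical providers".

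Other passages describe the opioid population differently:

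- Precis, population list: "discontinued from opioid medications at the request of their VA provider".
- Section 4, opening paragraph: "All eligible Veterans must be a prior persistent opioid user who was removed from their opioid medication by their VA provider".
- Aim 2 in the Precis: "polymorbid CMP Veterans discharged off of opioid medication in VA care since the start of the OSI".
- Section 2.2: Veterans "who are currently using chronic opioid therapy for pain", and later in the same paragraph "this study altered the opioid inclusion criterion to include Veterans who were removed from opioid medications during the OSI".
- Section 3: the second objective refers to persistent use that is recent and still going on, and the recruitment target refers to persistent use.

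**Who decides.** Section 6.2.1 gives the final eligibility decision to the PI and Co-Investigators, with the PI adjudicating unclear cases. Section 6.2.2 allows randomisation only once every inclusion and exclusion criterion is satisfied.

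**The concern.** Aim 2 asks whether Veterans return to opioids, a question that makes sense only in people who have stopped. A screening threshold that requires heavy use over the most recent three months works against that: the longer a Veteran has been off opioids, the more surely the row rejects them. The era rules are more direct, because inclusion 4 lets in a group that exclusion 3 removes entirely.

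Two things are at stake. Staff who apply the screening table and staff who apply Section 4.1 would accept different candidates. And a reader of the results could not tell from the plan which Veterans the findings on disability and recidivism describe.

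**Working it through.** The plan gives no figure to reproduce here. The check is a comparison of rules, plus day-counting for the opioid row.

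**Service era**

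1. Take a Veteran whose pain arose in Gulf War service and has no later link. Inclusion 4 is met.
2. The pain is unrelated to OEF/OIF/OND service, so exclusion 3 is met. The interview row is failed.
3. Section 6.2.2 requires all criteria to be satisfied, so the Veteran cannot be randomised. Exclusion 3 is not ambiguous, so adjudication of unclear cases does not reach it.
4. A Veteran whose pain was made worse in OEF/OIF/OND service satisfies inclusion 4 and escapes exclusion 3. The conflict is confined to Gulf War-only pain.

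**Opioid status: inputs**

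- TLFB row: 20 use days in 30, for the past 3 months (taken as 90 days).
- Criterion 6: at least 7 days off before the programme, no maximum.
- Section 6.2.2: up to 4 weeks (28 days) from enrolment to baseline, and up to 2 weeks (14 days) from baseline to treatment.

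**Longest time off at screening that still passes the row.** Assume use on every day before stopping, which is the most favourable case.

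- 20 of 30 in each 30-day block, or in every rolling 30-day window: 30 − 20 = 10 days.
- Pooled over three months (60 of 90): 90 − 60 = 30 days.

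**Longest time off at programme start**, with no use after screening:

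- Maximum gap: 28 + 14 = 42 days.
- By block: 10 + 42 = 52 days. Pooled: 30 + 42 = 72 days.

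**Both rules side by side**, for a Veteran with earlier chronic use and no use between screening and the programme:

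| Days off at screening | Criterion 6 | Row, by block | Row, pooled |
|---|---|---|---|
| 7 to 10 | met | met | met |
| 11 to 30 | met | failed | met |
| 31 or more | met | failed | failed |

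A Veteran six months or a year off opioids meets criterion 6 and fails the row on both readings. If discharged in VA care since the Opioid Safety Initiative began, that Veteran is also in the group Aim 2 names.

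**The case against.** The best defence is that Section 4 governs. Section 4.1 says its criteria must all be met, Section 6.2.2 ties randomisation to them, and the screening table labels each row by the criterion it serves. On that view the TLFB row is a loose restatement of the prior-use definition. The Precis supports this: its population list also refers to the past three or more months while describing Veterans already discontinued, and its design paragraph speaks of prior persistent use. Section 9.5.2 describes a 30-day TLFB calendar, which could not by itself verify three months of use, so the row may not have been applied literally.

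This is a fair account of what may have been intended, and it means the effect in practice is unknown. It does not remove the conflict. The row is written as a mandatory threshold, Veterans already off opioids are not exempted from it, and no visible text says which rule prevails. (Figure 3 and the screening forms in the appendices were not available.) Nor does it help with service era, where both conflicting rules lie within Section 4.

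The 42-day gap is a ceiling. Section 6.2.2 expects treatment generally within 5 weeks of enrolment; with 35 days the limits become 10 + 35 = 45 and 30 + 35 = 65. Accepting any single qualifying 30-day stretch would lengthen the limit further, but that strains the row's wording and would still leave a limit where criterion 6 has none.

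Stronger readings that a reader might infer are not supported:

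- *The two opioid rules exclude each other.* They overlap: a Veteran 7 to 10 days off at screening passes both, as can one still using at screening who stops at least a week before the programme.
- *The treatment comparison is biased.* Eligibility is settled before randomisation by one process for both arms.
- *The population is undefined.* Section 4.1 gives a definition; other passages disagree with it.
- *Permitted use before the programme will be counted as recidivism.* Section 9.6 does speak of a monthly comparison from baseline, but Section 9.2 counts 12 monthly follow-ups, and the phrase can simply mark the interval. At the scheduled Week 4/5 post-treatment visit, at most 2 days before the required opioid-free week fall within the look-back, below the threshold of 3.

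**Conclusion.** Both contradictions stand on current text, without relying on the revision history. The era conflict is absolute for Gulf War-only pain. The opioid conflict affects Veterans more than 10 days off opioids at screening, or more than 30 if use is pooled. At programme start the row implies a maximum of 52 (72) days off, assuming daily use before stopping, the full 42-day gap and no use in between.

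The consequence is that Veterans who meet the inclusion criterion in question can be screened out, and that the population to which Aims 1 and 2 apply is stated inconsistently. The documents contain no screening counts, so the share of candidates affected cannot be estimated. The passages need correcting because they cannot all be followed as written, and correction is cheap.

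**What to change.** 1. Reconcile the Precis (objectives, design and population), Sections 2.2, 3 and 4, exclusion 3 in Section 4.2, the Section 6.2.1 table and the aims in Section 9.6 to one opioid-status population and one service-era list. State also whether service in the era or deployment is required. The sponsor decides which wording governs.
2. Make the Section 6.2.1 thresholds refer to the Section 4 criteria.
3. Name that same population in Aim 2 and in the conclusions.
4. Report the number of screen failures for opioid status and for service era from the Enrollment Log, which under Section 4.3 records reasons for disqualification.
5. Optionally, add a line to Section 9.6 saying that the 12 monthly follow-ups, and not the baseline TLFB, are scored for recidivism.

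The cost is amendment wording and one count from an existing log, with no new visits or data collection. The log can answer the question only as far as reasons were recorded in that detail. Section 3 gives a 2014-2019 timetable and version 10.0 is dated September 2019. If enrolment has already closed, items 3 and 4 still matter for the report, because they tell readers whom the results describe.
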